9.2. Setting

Health care administrative claims and laboratory data will be provided by Komodo Health. Komodo Health uses artificial intelligence and data analytics to combine and link patient-level information from more than 150 payers in the United States, including Medicare, Medicaid, and Commercial plans.

Komodo Health will provide administrative claims data and HIV-related laboratory data available during January 1, 2014 through September 30, 2022 for individuals who have at least one ICD-9-CM or ICD-10-CM code related to HIV (Appendix Table 1) or at least one ART medication dispensed (Appendix Table 2).

9.2.1. Inclusion Criteria

To be eligible for the vaccine effectiveness study, individuals must meet the following criteria:

1. HIV infection defined as at least one inpatient International Classification of Diseases, Ninth Revision, Clinical Modification (ICD-9-CM) or International Classification of Diseases, Tenth Revision, Clinical Modification (ICD-10-CM) code related to HIV (Appendix Table 1) or ≥ 2 outpatient ICD-9-CM or ICD-10-CM codes related to HIV at least 30 days, but no more than 730 days apart, during January 1, 2014 and December 31, 2021

AND

2. At least 18 years of age at the time of the first recording of HIV-related ICD-9-CM or ICD-10-CM code

PFIZER CONFIDENTIAL

CT24-WI-GL02-RF02 5.0 Non-Interventional Study Protocol Template For Secondary Data Collection Study 01-Aug-2023

AND

[figure not shown]
3. At least six months of continuous enrollment in medical and pharmacy plans after the first HIV-related ICD-9-CM or ICD-10-CM code between January 1, 2014 and December 31, 2021. A gap of 30 days or less in enrollment will be allowed during this six month period.

9.2.2. Exclusion Criteria

Patients meeting the following criterion will not be included in the study:

1. Evidence of PCV13 vaccination before the first HIV-related ICD-9-CM or ICD-10-CM code

Figure 1. Illustrative timeline for study participants

PFIZER CONFIDENTIAL

CT24-WI-GL02-RF02 5.0 Non-Interventional Study Protocol Template For Secondary Data Collection Study 01-Aug-2023
Page 16 of 46

9.3. Variables

Table 1. Variables, definitions, and measurement periods

Variable type	Variable	Definition	Measurement period
Exposure	PCV13 vaccination	Current procedural terminology® (CPT) codes and National Drug Codes (NDC) listed in Appendix Table 3	Follow-up
Primary outcomes	IPD	ICD-9-CM or ICD-10-CM codes listed in Appendix Table 4	Follow-up
	Pneumococcal pneumonia	ICD-9-CM or ICD-10-CM codes listed in Appendix Table 4	Follow-up
	All-cause pneumonia	ICD-9-CM or ICD-10-CM codes listed in Appendix Table 4	Follow-up
	Pneumococcal pneumonia or pneumonia with unspecified causes	ICD-9-CM or ICD-10-CM codes listed in Appendix Table 5	Follow-up
	Pneumonia with unspecified causes	ICD-9-CM or ICD-10-CM codes listed in Appendix Table 5	Follow-up
Covariates	Age	Calculated as [year individual meets HIV criteria] – [birth year] Categorized as 18-49, 50-64, 65-74, and ≥ 75 years	Baseline
	Sex	Male, Female, Other, Unknown	Baseline
	Social Vulnerability Index (SVI)	SVI characterizes resiliency of a community when faced by external pressures and stresses [25, 26]. SVI ranges from 0 to 100, where a value of 100 indicates the most vulnerable population. SVI will be estimated using zip code and will be categorized as low (lowest quartile), average (middle two quartiles) and high (highest quartile).	Baseline
	Payor	Medicaid/CHIP, Medicare, Commercial, Dually eligible, Other, Unknown	Baseline
	US region	Northeast, North Central, South, West, Unknown	Baseline

Variable type	Variable	Definition	Measurement period
	Index year	Calendar year of first HIV diagnosis code	Baseline
	Alcoholism	ICD-9-CM or ICD-10-CM codes listed in Annex Table 1.1	Baseline and follow-up
	Asplenia	CPT/Healthcare Common Procedure Coding System (HCPCS), ICD-10-Procedure Coding System (ICD-10-PCS), ICD-9-Procedure Coding System (ICD-9-PCS), ICD-9-CM, or ICD-10-CM codes listed in Annex Table 1.2	Baseline and follow-up
	Asthma	ICD-9-CM or ICD-10-CM codes listed in Annex Table 1.3	Baseline and follow-up
	Chronic heart disease	CPT/HCPCS, ICD-10-PCS, ICD-9-PCS, ICD-9-CM, or ICD-10-CM codes listed in Annex Table 1.4	Baseline and follow-up
	Chronic kidney disease and renal failure	CPT/HCPCS, ICD-10-PCS, ICD-9-PCS, ICD-9-CM, or ICD-10-CM codes listed in Annex Table 1.5	Baseline and follow-up
	Chronic liver disease	CPT/HCPCS, ICD-10-PCS, ICD-9-PCS, ICD-9-CM, or ICD-10-CM codes listed in Annex Table 1.6	Baseline and follow-up
	Chronic lung disease	ICD-9-CM or ICD-10-CM codes listed in Annex Table 1.7	Baseline and follow-up
	Cigarette smoking	ICD-9-CM or ICD-10-CM codes listed in Annex Table 1.8	Baseline and follow-up
	Diabetes mellitus	ICD-9-CM or ICD-10-CM codes listed in Annex Table 1.9	Baseline and follow-up
	Generalized malignancy	CPT/HCPCS, ICD-10-PCS, ICD-9-PCS, ICD-9-CM or ICD-10-CM codes listed in Annex Table 1.10	Baseline and follow-up
	Hodgkin's lymphoma	ICD-9-CM or ICD-10-CM codes listed in Annex Table 1.11	Baseline and follow-up
	Immunosuppressive medications	PLWH will be considered on immunosuppressive medications if:	Baseline and follow-up

Variable type	Variable	Definition	Measurement period
		1) ≥1 NDC, HCPCS, or ICD-10-PCS code in Appendix Table 6 2) ≥ 1 NDC (using orals only) in Appendix Table 6 where the daily dose is ≥ 20mg or prednisone or prednisone equivalent for a duration of ≥14 consecutive days	
	Leukemia	ICD-9-CM or ICD-10-CM codes listed in Annex Table 1.12	Baseline and follow-up
	Multiple myeloma	ICD-9-CM or ICD-10-CM codes listed in Annex Table 1.13	Baseline and follow-up
	Nephrotic syndrome	ICD-9-CM or ICD-10-CM codes listed in Annex Table 1.14	Baseline and follow-up
	Non-Hodgkin's lymphoma	ICD-9-CM or ICD-10-CM codes listed in Annex Table 1.15	Baseline and follow-up
	Organ transplant	CPT/HCPCS, ICD-10-PCS, ICD-9-PCS, ICD-9-CM or ICD-10-CM codes listed in Annex Table 1.16	Baseline and follow-up
	Sickle cell disease or other hemoglobinopathies	ICD-9-CM or ICD-10-CM codes listed in Annex Table 1.17	Baseline and follow-up
	Hepatitis B	ICD-9-CM or ICD-10-CM codes listed in Annex Table 2.1	Baseline and follow-up
	Hepatitis C	ICD-9-CM or ICD-10-CM codes listed in Annex Table 2.2	Baseline and follow-up
	Annual physical exam	CPT/HCPCS codes listed in Annex Table 3.1	Baseline and follow-up
	Annual influenza vaccine	CPT/HCPCS, ICD-10-PCS, ICD-9-PCS, or NDC codes listed in Appendix Table 7	Baseline and follow-up
	Any pneumonia infection	ICD-9-CM or ICD-10-CM codes listed in Appendix Table 4	Baseline
	Any hospitalization	Evidence of inpatient claims	Baseline and follow-up
	Opportunistic infections	ICD-9-CM or ICD-10-CM codes listed in Appendix Table 14	Baseline and follow-up
	ART adherence	ART use will be identified by NDC codes listed in Appendix Table 2	Baseline and follow-up

Variable type	Variable	Definition	Measurement period
		
Adherence will be measured as 'Proportion of days covered = (Number of days covered by any ART, excluding ritonavir and cobicistat) ÷ (total days)*100'[27] every six months
 
Individuals with >80% of days covered will be classified as 'adherent' and individuals with ≤80% of days covered will be classified as 'non-adherent'[27]
	
	CD4 cell count	Categorized as <200, 200-499, ≥500 cells/mm ³	Baseline and follow-up
	PPSV23 vaccination	NDC and CPT codes listed in Appendix Table 8	Baseline and follow-up
	Annual CD4 laboratory test	
CD4 laboratory tests will be identified by CPT codes listed in Appendix Table 9
 
Individuals who have at least one CD4 laboratory test performed during each year of follow-up
	Baseline and follow-up
	Annual viral load laboratory test	
Viral load laboratory tests will be identified by CPT codes listed in Appendix Table 10
 
Individuals who have at least one viral load laboratory test performed during each year of follow-up
	Baseline and follow-up
	Respiratory virus season	Respiratory virus season occurs between October 1 and April 30	Follow-up
Sensitivity analysis outcome	All-cause pneumonia not associated with HIV	ICD-9-CM or ICD-10-CM codes listed in Appendix Table 11	Follow-up

9.4. Data Sources

The source of data for the VE study will be health care administrative claims and HIV-laboratory data provided by Komodo Health. Komodo Health uses artificial intelligence and

PFIZER CONFIDENTIAL

CT24-WI-GL02-RF02 5.0 Non-Interventional Study Protocol Template For Secondary Data Collection Study

01-Aug-2023

Page 20 of 46

data analytics to combine and link patient-level information from more than 150 payers in the United States, including Medicare, Medicaid, and Commercial plans. Currently, Komodo Health has patient-level data on approximately 325 million individuals and these data include inpatient and outpatient claims, pharmacy dispensing claims, provider specialty claims, and mortality information.

Komodo Health will provide administrative claims available between January 1, 2014 through September 30, 2022 for individuals who have at least one ICD-9-CM or ICD-10-CM code related to HIV (Appendix Table 1) or at least one ART medication dispensed (Appendix Table 2).

9.5. Study Size

The planned analyses do not involve hypothesis testing and sample size calculations are not applicable. However, we examined the precision of PCV13 vaccine effectiveness for IPD and all-cause pneumonia among people living with HIV at 36 months and 97 months (which was the maximum follow-up time available from feasibility assessments) after index (Table 2 and Table 3). Komodo Health provided the following information for the precision estimates:

- 175,000 individuals had ≥ 1 inpatient or ≥ 2 outpatient HIV ICD-9-CM or ICD-10-CM code diagnosis codes between January 1, 2014 and December 31, 2021
- 56,000 (32%) of these individuals received PCV13 after their first HIV diagnosis code

The following assumptions regarding incidence and PCV13 VE for IPD and all-cause pneumonia were used:

- IPD incidence among PLWH is 183 cases per 100,000 population [28]
- All-cause pneumonia incidence among PLWH is 5,487 cases per 100,000 population
- VE for IPD due to any serotype ranges from 7.5% to 22.5%
 - Published VE estimates for vaccine type IPD range from 25% to 75% [20]. Because one-third of the adult IPD burden is considered PCV13 type [29], we multiplied this range by 30% to arrive at 7.5% to 22.5%
- VE for all-cause pneumonia ranges from 5% to 15% [30]
- Annual censoring of individuals due to loss to follow-up or death may range between 4% or 10%

Survival and censoring times were simulated assuming exponential distributions. Vaccination status was modelled as a time-varying covariate [31]. Hazard ratios were assumed as $1 - (VE/100)$. Simulations were run 100 to 200 times per scenario. Cox regression models were run on each simulated dataset to estimate the 95% confidence

PFIZER CONFIDENTIAL

intervals (CI) for the log HRs. Means were generated and exponentiated to obtain the 95% CIs for the VEs using $(1 - HR) \times 100$ and used to describe VE precision.

Table 2. Precision of PCV13 vaccine effectiveness estimates for invasive pneumococcal disease

Hypothesized Vaccine Effectiveness (%)	36 months of follow-up			97 months of follow-up		
	Lower 95% confidence interval estimate	Upper 95% confidence interval estimate	Total number of events	Lower 95% confidence interval estimate	Upper 95% confidence interval estimate	Total number of events
Scenario #1 – 4% annual censoring						
7.5	-12	25	837	-5	19	1492
22.5	3	37	817	11	33	1452
Scenario #2 – 10% annual censoring						
7.5	-15	25	766	-6	21	1272
22.5	2	38	752	9	33	1224

Table 3. Precision of PCV13 vaccine effectiveness estimates for all-cause pneumonia

Hypothesized Vaccine Effectiveness (%)	36 months of follow-up			97 months of follow-up		
	Lower 95% confidence interval estimate	Upper 95% confidence interval estimate	Total number of events	Lower 95% confidence interval estimate	Upper 95% confidence interval estimate	Total number of events
Scenario #1 – 4% annual censoring						
5	1	9	23,370	2	7	38,848
15	11	19	23,119	13	17	38,176
Scenario #2 – 10% annual censoring						
5	1	9	21,558	2	8	33,257
15	11	19	21,327	12	18	32,750

Given the precision estimates in Tables 1 and 2, the planned study should have adequate precision to address the primary objectives.

9.6. Data Management

Komodo will create analytic files comprising people who have at least one HIV related ICD-9-CM or ICD-10-CM code or claim for an ART medication to treat HIV. The analytic files will include person-level data, including information on baseline demographic and clinical characteristics, study outcomes, and health plan enrollment dates. Variables will be created based on information from healthcare claims and enrollment information, which will be

PFIZER CONFIDENTIAL

CT24-WI-GL02-RF02 5.0 Non-Interventional Study Protocol Template For Secondary Data Collection Study

01-Aug-2023

Page 22 of 46

linked at the person level using a unique ID, which is deidentified. Data for this study will be processed and managed by Pfizer, Inc., and all analyses—as described in the final version of the Study Protocol—will be directed by study investigators.

Retention of study-related data, documents, and other materials will be governed by Pfizer Policy on Records and Information Management, and per this policy, will remain effective for a period of 5 years from the date of project initiation. Amendments must be made only with the prior approval of Pfizer. Agreement from all study collaborators must be obtained for all amendments.

9.7. Data Analysis

Cox proportional hazards models will be used to estimate the hazard ratio (HR) for each outcome comparing vaccinated PLWH with unvaccinated (no PCV13) PLWH. To explore potential changes in VE over time, HRs will also be generated during specific time periods (0-3, 3-5, 5-7 years of follow-up) using piecewise Cox regression models, if there is adequate sample size. All models will be adjusted for time-fixed and time-varying covariates of interest using inverse probability of treatment weighting. The time-fixed covariates of interest include sex, age, payor, SVI, previous pneumonia infection, and hospitalization and will be measured during the baseline period. The time-varying covariates include risk factors for pneumonia (alcoholism, asplenia, asthma, chronic heart disease, kidney, liver, and lung diseases, cigarette smoking, diabetes, immunosuppressive conditions and medications, and sickle cell disease), annual physical exams, annual influenza vaccine, hospitalization, opportunistic infections, ART adherence, annual CD4 and viral load laboratory tests, and an indicator for respiratory virus season.

VE will be calculated as 1 minus the estimated HR for each outcome.

We will conduct two sets of analyses for each outcome. In the first set, we will examine the first event for each outcome and in the second set, all recurrent outcome events during follow-up will be included. In the first set of analyses, unvaccinated (no PCV13) PLWH will be followed from index date until the earliest occurrence of the following: outcome, PCV13 vaccination, death, end of health plan enrollment, or end of study period, and vaccinated PLWH will be followed from 14 days after vaccination date, or index date if vaccinated during the baseline period, until the earliest occurrence of outcome, death, end of health plan enrollment, or end of study period. In the second set of analyses unvaccinated (no PCV13) PLWH will be followed from index date until the earliest occurrence of PCV13 vaccination, death, end of health plan enrollment or end of study period and vaccinated PLWH will be followed from 14 days after vaccination date, or index date if vaccinated during the baseline period, until earliest occurrence of death, end of health plan enrollment, or end of study period.

Several stratified analyses will be conducted. PPSV23 is recommended for PLWH and feasibility data provided by Komodo suggest that one in four PWLH who received PCV13 during 2014-2015 also received PPSV23 within two years. Rather than censor or exclude

individuals who receive PPSV23, we will calculate PCV13 VE among PWLH who have/have not received PPSV23 before and during the study period.

Feasibility assessments from Komodo indicate that approximately 25% of PWLH have at least one CD4 cell count or percentage laboratory result available. Therefore, we will calculate PCV13 VE among the subset of PWLH who have a CD4 cell count during the baseline period or follow-up, and potentially stratify by CD4 category using each patient's lowest value during the study.

Additional VE stratifications by ART adherence during follow-up, year of HIV diagnosis, and age will be assessed for feasibility as well, as these affect patients' immune status and immune reconstitution. Due to possible waning of the VE and different lengths of follow-up by index year, VE stratification by year of HIV diagnosis will be restricted to the first 3 years of follow-up.

A sensitivity analysis will also be conducted. In this analysis, causes of pneumonia that are characteristic of HIV, for example pneumonia due to cytomegalovirus, mycobacteria, and fungi, will be excluded from our definition of all-cause pneumonia.

Residual confounding of our VE estimates due to inadequate control for health care seeking behavior and immune status in our analyses will be explored. To do so, we will employ a negative control exposure and a negative control outcome. Potential negative control exposures include vaccinations that are recommended for PLWH but would not be expected to have any protective effect against the pneumonia outcomes of interest. If residual confounding does not exist, the negative control vaccine would not have an effect on the pneumonia outcomes. However, if the analysis demonstrates that the negative control vaccine protects against these outcomes, this suggests the presence of residual confounding.

Similarly, potential negative control outcomes are outcomes that share the same sources of biases as the primary outcomes in our study population but are not causally-related to PCV13 vaccination. For example, immune status is an important predictor of pneumonia outcomes among PLWH, but we will be missing CD4 laboratory values for most of our study population. In order to detect potential residual confounding by lack of control for immune status, a potential negative control outcome could include a more common AIDS defining illness such as candidiasis. Again, if no residual confounding exists, PCV13 vaccination would have no effect on the occurrence of the negative control outcomes. However, if the results suggest that PCV13 vaccination prevents the negative control outcomes, residual confounding may exist.

Detailed methodology for summary and statistical analyses of data collected in this study will be documented in a statistical analysis plan (SAP), which will be dated, filed and maintained by the sponsor. The SAP may modify the plans outlined in the protocol; any major modifications of primary endpoint definitions or their analyses would be reflected in a protocol amendment.

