### 5.2.3. Subgroups and Stratification

*Several stratified analyses will be conducted. PPSV23 is recommended for PLWH and feasibility data provided by Komodo suggest that one in four PWLH who received PCV13 during 2014-2015 also received PPSV23 within two years. Rather than censor or exclude individuals who receive PPSV23, we will calculate PCV13 VE among PWLH who have/have not received PPSV23 before and during the study period. The analysis may also be stratified by the number of PPSV23 doses, e.g. 0, 1, 2+.*

*Feasibility assessments from Komodo indicate that approximately 25% of PWLH have at least one CD4 cell count or percentage laboratory result available. Therefore, we will calculate PCV13 VE among the subset of PWLH who have a CD4 cell count during the baseline period or follow-up, and potentially stratify by CD4 category using the patient's lowest value during the study.*

*Additional VE stratifications by ART adherence during follow-up, year of HIV diagnosis, and age will be assessed for feasibility as well, as these affect patients' immune status and immune reconstitution. Due to possible waning of the VE and different lengths of follow-up by index year, VE stratification by year of HIV diagnosis will be restricted to the first 3 years of follow-up (0 to 1079 days).*

The above subgroup analyses will be conducted if there are sufficient numbers of patients/events to maintain patient de-identification (Section 5.8.3) and where the 95% confidence intervals (CI) for the VE estimates can be expected to exclude zero in the best case scenarios for the analyses, i.e. the highest expected VE estimate, the lowest expected censoring rate and at the maximum follow-up time. Table 5.1 provides precision estimates for IPD and all-cause pneumonia under different numbers of individuals available for the analysis. The following assumptions were used for the estimates:

- 32% of individuals received PCV13
- IPD incidence among PLWH is 183 cases per 100,000 population [1]
- All-cause pneumonia incidence among PLWH is 5,487 cases per 100,000 population
- VE for IPD due to any serotype is 22.5% [2, 3]
- VE for all-cause pneumonia is 15% [4]

- Annual censoring of individuals due to loss to follow-up or death is 4%
- Up to 97 months of follow-up

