### 5.3.2. Covariates

The list of demographic and clinical characteristics considered for descriptive reporting, subgroups and inclusion as covariates in models for generating the propensity scores are provided in Table 5.3. The Komodo Health database will be source of all variables.

Patients will be considered to have a comorbidity or hospitalization during baseline if there was evidence of a diagnosis at any time during the baseline period. Evidence of comorbidities or hospitalization during follow-up will be considered as new diagnoses. Once diagnosed, patients will be considered diagnosed for the remainder of their follow-up. ART adherence during baseline and follow-up will be updated every 6 months (180 days) based on the data collected in that previous timeframe. For baseline annual physical exam and annual influenza vaccine, patients will be considered adherent (coded as 'Yes') if there was evidence of these events at any time during the baseline period. During the follow-up, patients will be considered adherent up to 365 days after the last event date.

For annual CD4 and viral load laboratory tests during baseline and follow-up, patients will be coded as 'Yes' up to 365 days after the last event date. For respiratory virus season during follow-up, patients will be coded as 'Yes' if the observation time is in October, November, December, January, February, March or April.

The baseline period for the assessment of covariates is the six months prior to the index date, i.e., no data prior to six months will be included.

Covariates used at baseline only will be considered time-fixed confounders. Covariates additionally or only used during follow-up will be considered time-varying confounders.

Categories may be collapsed, or covariates may be excluded from the propensity scores if models fail to converge.

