Any hospitalization	Evidence of inpatient claim(s) Yes, No	Descriptive, covariate	Baseline and follow-up
Hodgkin's lymphoma	ICD-9-CM or ICD-10-CM codes listed in Protocol Annex 1.11 Yes, No	Descriptive, covariate	Baseline and follow-up
Opportunistic infections	ICD-9-CM or ICD-10-CM codes listed in Protocol Annex Table 14	Descriptive, covariate	Baseline and follow-up

	Yes, No  Note: In the analysis of all-cause pneumonia, pneumocystis jirovecii pneumonia codes are excluded from the follow-up. In the analysis of candidiasis negative control outcomes, candidiasis infection codes are excluded from the follow-up.		
Antiretroviral treatment (ART) adherence	ART use will be identified by NDC codes listed in Appendix Table 7.2  Adherence will be measured as 'Proportion of days covered = (Number of days covered by any ART, excluding ritonavir and cobicistat) ÷ (total days)*100'[8] every six months  Individuals with >80% of days covered will be classified as 'adherent' and individuals with ≤80% of days covered will be classified as 'non-adherent'[8]. Individuals without ART information will be classified as Missing. As a subgroup, ART adherence will be calculated using the information over the entire follow-up.	Descriptive, covariate, subgroup	Baseline and follow-up
CD4 cell count	Categorized as <200, 200-499, ≥500 cells/mm 	Descriptive, subgroup	Baseline and follow-up
PPSV23 vaccination	NDC and CPT codes listed in Appendix Table 7.9  Yes, No. 0, 1, 2+ doses	Descriptive, subgroup	Before first HIV diagnosis, baseline and follow-up
Annual CD4 laboratory test	CD4 laboratory tests will be identified by CPT codes listed in Appendix Table 7.11  Individuals who have at least one CD4 laboratory test performed during each year of follow-up Yes, No	Covariate	Baseline and follow-up
Annual viral load laboratory test	Viral load laboratory tests will be identified by CPT codes listed in Appendix Table 7.12  Individuals who have at least one viral load laboratory test performed during each year of follow-up Yes, No	Covariate	Baseline and follow-up

Respiratory virus season	Respiratory virus season occurs between October 1 and April 30 Yes, No	Covariate	Follow-up
--------------------------	---	-----------	-----------

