weights after vaccination will be constant. Time-varying covariates will be lagged, i.e., within each 30-day (or 90-day for RZV) interval the vaccination status will be the status at the end of the interval, whereas the values for the covariates will be from the end of the previous interval. Cox proportional hazards models will be used to model the associations between vaccination status and the numerators and denominators.

It is possible that censoring may be informative, with patient characteristics associated with loss to follow-up. Therefore, patients who are censored may have different risks of the study outcomes than patients who are not censored. Inverse probability of censoring weighting (IPCW) will also be generated during the follow-up using the above methods for IPTW. These weights will be multiplied by the IPT weights to produce a new set of weights [9].

Distributions of the IPT, IPC and IPT\*IPC weights will be summarized by vaccination status. In the presence of extreme/outlier weights, stabilized weights may be truncated at the 1st and 99th percentiles for use in the Cox models for the outcomes. Although there is no formal definition of an extreme weight, the need for truncation will be judged based on the distributions and the potential effect on the interpretation of results [9].

Weights for first and recurrent events will be generated separately in datasets created for each study outcome; however, all weights will be derived without assessing their impact on the VE estimates. Weights will also be generated again in each of the subgroups. The weights will be generated using the *ipwtn* function within the *ipw* R package [10]. Example R code is provided in Appendix 7.2.

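### CD4-subset entry, lowest-CD4 strata and whole-follow-up ART strata can use information recorded after vaccination, and in part after the outcome, so VE within them can be biased in either direction

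*Protocol*

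**What the plan says.** Protocol 9.7 says that VE will be calculated in "the subset of PWLH who have a CD4 cell count during the baseline period or follow-up", and that the analysis may "potentially stratify by CD4 category using each patient's lowest value during the study". SAP 5.2.3 repeats the rule: "potentially stratify by CD4 category using the patient's lowest value during the study". The categories are <200, 200-499 and ≥500 cells/mm³.

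On ART, Protocol 9.7 says: "Additional VE stratifications by ART adherence during follow-up, year of HIV diagnosis, and age will be assessed for feasibility". SAP Table 5.3 gives the subgroup rule: "As a subgroup, ART adherence will be calculated using the information over the entire follow-up".

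The main model treats the same kind of information differently. SAP 5.3.2 says: "ART adherence during baseline and follow-up will be updated every 6 months (180 days) based on the data collected in that previous timeframe". SAP 5.8.4 says: "Time-varying covariates will be lagged". CD4 value is listed in SAP Table 5.3 as a descriptive and subgroup variable only, so it does not enter the weights. The one provision specific to subgroups is in SAP 5.8.4: "Weights will also be generated again in each of the subgroups".

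**The concern.** PCV13 is a time-varying exposure that can be received during follow-up (SAP 5.8.4). Overall follow-up runs from index to death, disenrollment or study end (SAP 5.8.9). Neither the CD4 window nor the ART window is stated to close at vaccination, and the CD4 window does not close at the outcome.

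Three things follow.

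- A patient can enter the CD4 subset because of a test done at or after a pneumonia episode, and that test can also set the lowest value.
- The lowest of several values falls as the number of tests rises, so the stratum depends on length of follow-up and on care seeking. The sponsor's reason for adding the annual CD4-test covariate was that HIV care seeking differs by vaccination status (Protocol section 5, version 2.0).
- A patient vaccinated at a high CD4 whose count falls years later is placed in the low stratum for all of follow-up.

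Conditioning on membership defined in this way can change the hazard ratio even when true VE is the same in everyone. Weights refitted inside the group balance measured covariates among those already selected; they do not undo selection on later information. The limitations in Protocol 9.9 do not mention this. At stake is whether VE in the CD4 subset and in the CD4 and ART strata can be read at face value.

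**Working it through.** **1. Reproduce the plan's precision figure.** The CD4 subset is about 25% of 175,000, or 43,750 patients, which is close to the 43,000 (N/4) row of SAP Table 5.1. That row gives -5% to 41% for IPD (VE 22.5%) and 10% to 20% for all-cause pneumonia (VE 15%).

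- Protocol Table 2 (VE 22.5%, 97 months, 4% censoring) gives 11% to 33% with 1,452 events. SE of log HR = [ln(0.89) - ln(0.67)] / (2 × 1.96) = 0.0724.
- Implied p(1-p) = 1 / (0.0724² × 1,452) = 0.131. With the 38,176 all-cause events of Protocol Table 3, SE = 1/√(0.131 × 38,176) = 0.0141.
- Multiply each SE by √(175,000/43,000) and use CI = 1 - (1 - VE) × exp(±1.96 SE).
- Result: IPD -3.2% to 41.8%; all-cause 10.1% to 19.6%.

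This agrees with the table within about 2 points. It is a scaling check, not a rerun of the simulation.

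**2. Placement that depends on the outcome, equal in both arms.** Inputs from the documents: incidence λ = 0.05487 per year and VE 15%, so λ = 0.05487 × 0.85 = 0.04664 in the vaccinated. Assumptions: T = 5 years, exposure fixed from time zero, a share p0 = 15% of event-free people in the low stratum, and a share p1 of people with an event.

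- Probability of an event: P = 1 - e^(-λT)
- Time contributed by people with an event: A = [1 - e^(-λT)(1 + λT)] / λ
- Time contributed by event-free people: B = T e^(-λT)
- Rate in the low stratum: P·p1 / (A·p1 + B·p0)

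Unvaccinated: P = 0.2399, A = 0.5724, B = 3.8003. Vaccinated: P = 0.2080, A = 0.4998, B = 3.9600. For p1 = 30% the rates are 0.0720/0.7418 = 0.0970 and 0.0624/0.7439 = 0.0839, so VE = 1 - 0.0839/0.0970, which is 13.6% with unrounded rates.

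| p1 | VE, low stratum | VE, rest |
|---|---|---|
| 15% (= p0) | 15.0% | 15.0% |
| 30% | 13.6% | 15.3% |
| 40% | 12.8% | 15.5% |
| 60% | 11.4% | 15.9% |

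At 8 years the low stratum reads 12.9%, 11.9% and 10.2% for the last three rows. With p1 = p0 there is no bias.

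**3. Testing that also depends on vaccination.** First events were simulated with time-varying vaccination, a true VE of 15% in everyone and no confounding; the full simulated cohort reads 14.8%. Assumptions not in the documents: routine test rate about 0.045 per year, and tests triggered by the outcome read 150 cells lower. The columns give the share of outcomes that trigger a test. Entries are VE in the subset with any CD4.

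| Routine testing after vaccination | 0% | 10% | 25% | 50% |
|---|---|---|---|---|
| unchanged | 15.7% | 15.2% | 14.6% | 13.4% |
| ×1.25 | 14.8% | 17.4% | 18.9% | 19.6% |
| ×1.5 | 14.6% | 19.2% | 22.9% | 25.0% |
| ×2 | 14.6% | 22.1% | 28.0% | 32.3% |

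In the stratum with lowest value <200, the 10/25/50% columns read 13.6/12.6/10.4% with unchanged testing and 26.7/30.1/30.4% with testing doubled. With unchanged testing, 38/52/66% of that stratum had the outcome, against 18% overall. Monte Carlo SEs are 0.2-0.7 points for the subset and up to 3 points for the <200 stratum.

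**4. Membership fixed before follow-up.** Restricting to patients with a baseline CD4, with testing doubled and a 25% trigger, the simulation gives 14.9% (Monte Carlo SE 0.8). The routine test rate was raised to 0.5 per year in this run so that enough patients had a baseline count.

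**The case against.** The best reply is that these analyses are limited and gated. The CD4 strata are only potentially planned and the ART strata are subject to feasibility. SAP 5.2.3 runs a subgroup only where the best-case interval excludes zero. At N/4 the IPD interval is -5% to 41%, so the CD4 subset would not be run for IPD. All of this stands. The analysis of the any-CD4 subset is, however, stated firmly in Protocol 9.7, and all-cause pneumonia passes the gate.

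The shift in step 2 is also small: 1.4 to 3.6 points, against a half-width of about 8 points for one third of the CD4 subset (about 14,600 patients, roughly 6.4% to 22.8%). That stands for step 2. Under step 3, shifts in the whole subset range from negligible to 17 points, against a half-width of about 5.

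A reader might infer several stronger things that the documents do not support.

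- *VE is pulled toward zero at low CD4, giving a false picture of a weaker vaccine in the immunosuppressed.* This holds only if placement given event status is the same in both arms. Step 3 shows the opposite sign when it is not.
- *The plan defeats its stated aim of VE by immune status.* The sentence on immune status and reconstitution in Protocol 9.7 refers to ART adherence, year of diagnosis and age, not to the CD4 rule.
- *Time before the first CD4 is immortal.* It is time alive and enrolled, not time free of the outcome; an earlier pneumonia still counts.
- *ART strata always use data after the event.* First-event follow-up ends at the outcome (Protocol 9.7, SAP 5.8.4), so on that reading only the recurrent-event analyses do.
- *The Missing ART category removes untreated patients from the non-adherent stratum.* SAP Table 5.3 does not define being without ART information, so this is a request for clarification and not a demonstrated fault.

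**Conclusion.** The concern holds in limited form. Entry to the CD4 subset, and the CD4 and ART strata, can depend on information recorded after vaccination and, for CD4 (and for ART in recurrent-event analyses), after the outcome. Nothing in the plan corrects for this. VE in these groups can be biased in either direction, and neither sign nor size can be fixed from the documents: the placement shares and testing rates above are assumptions. The documents also do not say that pneumonia prompts CD4 tests or lowers CD4; they only leave the window open to it. A patient whose lowest value is the baseline one is classed correctly. The overall VE estimates are not affected, and it would be wrong to extend the point to them.

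**What to change.** In Protocol 9.7, SAP 5.2.3 and SAP Table 5.3, choose one of two rules.

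- **Fixed before follow-up.** Set the CD4 category from the last result on or before index, and the ART stratum from the baseline six-month proportion of days covered. Restrict the CD4 analysis to patients with a qualifying prior result. SAP 5.3.2 limits baseline covariate data to the six months before index, so state whether older CD4 results count. For patients vaccinated during baseline the value may still follow vaccination, but it precedes every counted outcome.
- **One lagged rule.** Use the most recent prior CD4 and the previous 180-day ART block, updated in the same way in vaccinated and unvaccinated person-time. Start a patient's time in the CD4 analysis at the later of index and first CD4 result. Do not freeze CD4 at vaccination while updating it in the unvaccinated: misclassification would then differ by exposure. State how the cumulative weights are handled when person-time moves between strata.

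Keep whole-study lowest CD4 and whole-follow-up adherence as descriptive only. Separately, define what counts as being without ART information.

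The data are already held, so the main cost is precision. The share with a baseline CD4 is not in the documents. Scaling as in step 1, an assumed 10% (17,500) gives an all-cause interval of about 7% to 22%, and an assumed 5% (8,750) about 4% to 25%. One of three equal strata of 17,500 gives about 1% to 27%. The lagged rule loses person-time before the first result but keeps more patients.
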